## Study Treatments

The options in the CCR treatment arm include:

- BSC only: continuous 28-day cycles of BSC. Best supportive care includes, but is not limited to, hydroxyurea for leukocytosis and/or differentiation syndrome associated with therapy of mutant IDH inhibition (ie, IDH differentiation syndrome), anti-infectives, analgesics, antiemetics, antipyretics, transfusions and nutritional support (refer to Section 7.1.5 and Section 8 for details);
- Azacitidine SC plus BSC: continuous 28-day cycles of azacitidine 75 mg/m^2/day SC for 7 days, plus BSC;
- LDAC SC plus BSC: continuous 28-day cycles of cytarabine 20 mg SC twice a day (BID) for 10 days, plus BSC;
- IDAC IV plus BSC: 28-day cycles of cytarabine 0.5 to 1.5 g/m^2/day IV for 3 to 6 days, per standard institutional practice, plus BSC; only BSC given after IDAC therapy concludes per standard institutional practice. (Note: any local standard regimen different from the above specification will need review and approval by the Medical Monitor.)

Subjects randomized to the AG-221 treatment arm will receive continuous 28-day cycles of AG-221 100 mg orally (PO) once a day (QD) for 28 days, plus BSC. Dose escalation to 200 mg may occur for augmenting treatment response (detailed in Section 7.2.1.2).

Study treatments as described above can continue until the End of Trial, unless discontinued for any of the reasons detailed in Section 11.1.

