### 3.1.2. Treatment Phase

Study treatment starts within 3 days after randomization. No crossover between any of the treatment options, including the CCR treatment options, will be permitted during the course of study treatment.

Assessments during study treatment include efficacy, safety, Health-related Quality-of-Life (HRQoL) questionnaires, [REDACTED].

A retrospective central review of all bone marrow aspirates and/or biopsies, peripheral blood smears and cytogenetics collected after the start of study treatment will be conducted by personnel blinded to subject treatment. The central cytogenetic review will provide standardized analysis and reporting for all subjects, regardless of the laboratory performing the initial analysis (local or central). The central assessments will be used in the statistical analyses. Disagreement between central and local assessments will be adjudicated by a third party reviewer and the adjudicated assessment will be used in the statistical analyses. Instructions for submission slides of bone marrow aspirate (and/or biopsy) and peripheral blood smear, and pertinent reports to central review are provided in the Study Reference Manual and Study Central Laboratory Manual.

Response to treatment and hematological improvement (HI) will be assessed by the investigators and by a blinded Independent Response Assessment Committee (IRAC) according to modified IWG AML Response Criteria ([Appendix F](#)) and IWG myelodysplastic syndromes (MDS) HI criteria ([Appendix H](#)), respectively.

Dosing interruptions, dosing delays or dose modifications may occur for managing toxicities and/or augmenting treatment response during study treatment (refer to Section 7.2 for details).

Subjects can continue to receive study treatment provided that they benefit from study treatment and all protocol-specified criteria for continuing study treatment are met. Study treatment will be discontinued if the investigator has alternative therapies (eg, HSCT) and/or considers the study treatment to be no longer beneficial to the subject, or the rapidity of change of disease state renders it unacceptable for further study treatment in the judgment of the investigator. Study treatment will be discontinued if females of childbearing potential (FCBPs) become pregnant during the study. Refer to Section 11 for events that are considered sufficient reasons for discontinuing a subject from study treatment.

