### IDH Differentiation Syndrome

Subjects treated with AG-221 (enasidenib) have experienced symptoms of differentiation syndrome, which can be fatal if not treated. Symptoms may include fever, dyspnea, acute respiratory distress, pulmonary infiltrates, pleural or pericardial effusions, rapid weight gain or peripheral edema, lymphadenopathy, bone pain, and hepatic or renal dysfunction. If differentiation syndrome is suspected, initiate corticosteroid therapy and hemodynamic monitoring until symptom resolution.

If differentiation syndrome is suspected, initiate oral or intravenous corticosteroids (eg, dexamethasone 10 mg every 12 hours) and hemodynamic monitoring until improvement. Taper corticosteroids only after resolution of symptoms. Symptoms of differentiation syndrome may recur with premature discontinuation of corticosteroid treatment. If severe pulmonary symptoms requiring intubation or ventilator support, and/or renal dysfunction persist for more than 48 hours after initiation of corticosteroids, interrupt enasidenib until signs and symptoms are no longer severe. Hospitalization for close observation and monitoring of patients with pulmonary and/or renal manifestation is recommended. Enasidenib can be resumed when signs and symptoms improve to Grade 2 or lower.

Further information on diagnosis and treatment of IDH differentiation syndrome can be found in the current version of IDH differentiation syndrome guidance documents.

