## 10. ADVERSE EVENTS

### 10.1. Monitoring, Recording and Reporting of Adverse Events

An AE is any noxious, unintended, or untoward medical occurrence that may appear or worsen in a subject during the course of a study. It may be a new intercurrent illness, a worsening concomitant illness, an injury, or any concomitant impairment of the subject's health, including laboratory test values (as specified by the criteria in Section 10.3), regardless of etiology. Any worsening (ie, any clinically significant adverse change in the frequency or intensity of a pre-existing condition) should be considered an AE. A diagnosis or syndrome should be recorded on the AE page of the eCRF rather than the individual signs or symptoms of the diagnosis or syndrome.

Abuse, withdrawal, sensitivity or toxicity to IP should be reported as an AE. Overdose, accidental or intentional, whether or not it is associated with an AE should be reported on the overdose eCRF. See Section 7.2 for the definition of overdose. Any sequela of an accidental or intentional overdose of study treatment should be reported as an AE on the AE eCRF. If the sequela of an overdose is an SAE, then the sequela must be reported on an SAE report form and on the AE eCRF. The overdose resulting in the SAE should be identified as the cause of the event on the SAE report form and eCRF but should not be reported as an SAE itself.

In the event of overdose, the subject should be monitored as appropriate and should receive supportive measures as necessary. There is no known specific antidote for overdose of IP. Actual treatment should depend on the severity of the clinical situation and the judgment and experience of the treating physician.

All subjects will be monitored for AEs during the study. Assessments may include monitoring of any or all of the following parameters: the subject's clinical symptoms, laboratory, pathological, radiological or surgical findings, physical examination findings, or findings from other tests and/or procedures.

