### **10.3. Abnormal Laboratory Values**

An abnormal laboratory value is considered to be an AE if the abnormality:

- results in discontinuation from the study;
- requires treatment, modification/ interruption of IP dose, or any other therapeutic intervention; or
- is judged to be of significant clinical importance, eg, one that indicates a new disease process and/or organ toxicity, or is an exacerbation or worsening of an existing condition.

Regardless of severity grade, only laboratory abnormalities that fulfill a seriousness criterion need to be documented as a SAE.

If a laboratory abnormality is one component of a diagnosis or syndrome, then only the diagnosis or syndrome should be recorded on the AE page/screen of the eCRF. If the abnormality was not a part of a diagnosis or syndrome, then the laboratory abnormality should be recorded as the AE. If possible, the laboratory abnormality should be recorded as a medical term and not simply as an abnormal laboratory result (eg, record thrombocytopenia rather than decreased platelets).

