11.2. Adverse Events of Special Interest

The following TEAEs of special interest will be summarized:

1. QT prolongation;
Standardized MedDRA Query (SMQ) Torsade de pointes/QT prolongation.
2. IDH inhibitor associated Differentiation syndrome (IDH-DS);
 - a. TEAE AE differentiation syndrome as reported by the investigators.
 - b. Time to IDH-DS: Summary statistics including mean, standard deviation, median, minimum, maximum will be provided.
 - i. From start of treatment until an event of IDH-DS
 - ii. From onset until end date of an event of IDH-DS
 - c. Signs and symptoms of PT IDH-DS (% of subject with specific symptom with denominator of N of subjects with completed CRF page for the differentiation syndrome).
 - Symptoms of the IDH-DS (from the CRF AE page)
 - Treatment for IDH-DS: systemic steroids
 - Mean duration of steroid treatment for the IDH-DS
 - Study drug interruption, discontinuation, dose adjustment due to IDH-DS
 - d. Concurrency of the IDH-DS and tumor lysis syndrome PT.
3. Bilirubinemia and liver safety;
 - a. SMQ Biliary system related investigations, signs and symptoms (narrow terms)
 - b. SMQ Drug related hepatic disorders (broad terms).
 - c. Time to onset and time to resolution
4. Hepatic Disorders;
5. Acute Renal Failure;
6. Pulmonary Events;
7. Peripheral Neuropathy
8. Hepatobiliary Disorders;

The following summaries will be provided for TEAEs of special interest:

- All TEAEs by PT;
- Treatment related TEAEs by PT;
- Serious TEAEs by PT;
- Serious treatment related TEAEs by PT;
- TEAEs with CTCAE grade of Grade ≥ 3 ;

- Treatment related TEAEs with CTCAE grade of Grade ≥ 3 ;
- Time to first onset of TEAE;

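### AG-221 organ events recorded as IDH differentiation syndrome probably drop out of the organ-specific AESI counts, tilting the between-arm comparison towards AG-221, chiefly for Pulmonary Events

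*SAP*

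**What the plan says.** **Recording.** Protocol 10.1 states: "A diagnosis or syndrome should be recorded on the AE page of the eCRF rather than the individual signs or symptoms". Protocol 10.3 extends this to laboratory findings: "If a laboratory abnormality is one component of a diagnosis or syndrome, then only the diagnosis or syndrome should be recorded".

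**The syndrome.** Protocol 7.2.1.3 describes IDH-DS: "Symptoms may include fever, dyspnea, acute respiratory distress, pulmonary infiltrates, pleural or pericardial effusions, rapid weight gain or peripheral edema". The list goes on to hepatic and renal dysfunction. The Study Treatments part of the Protocol Summary, where it describes best supportive care, ties the syndrome to mutant-IDH inhibitor therapy, and SAP 11.2 item 2 names it the same way. In CCR no such drug is study treatment, and Protocol 3.1.2 adds: "No crossover between any of the treatment options, including the CCR treatment options, will be permitted during the course of study treatment".

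**Analysis.** SAP 11.2 item 2 identifies the syndrome as "TEAE AE differentiation syndrome as reported by the investigators". Its symptoms are tabulated within that item only, with the number of subjects who have a completed differentiation syndrome CRF page as denominator. Hepatic Disorders (item 4), Acute Renal Failure (5), Pulmonary Events (6) and Hepatobiliary Disorders (8) are separate AESIs. Items 1 and 3 name standardized MedDRA queries (SMQs); items 4 to 8 name neither an SMQ nor a preferred-term (PT) list. Under SAP 11, safety summaries are presented by treatment and CCR option on the safety population.

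**The concern.** The recording rule is the same for everyone, but this particular diagnosis is in practice available in one arm only. A CCR subject with respiratory distress and infiltrates has pulmonary AEs on the form. An AG-221 subject with the same picture, diagnosed as IDH-DS, has a single syndrome term. The trial is open-label and the term is whatever the investigator reports, so knowledge of treatment helps decide which label is used. If the organ-specific AESIs are built from reported AE terms and nothing puts the syndrome's components back, the AG-221 counts for those organs are too low relative to CCR.

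At stake is a plain safety question: did more subjects on AG-221 than on CCR have a pulmonary, renal or hepatic event? The IDH-DS table cannot answer it, because that table has essentially no CCR comparator and its symptom percentages do not use the arm as denominator.

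**Working it through.** The plan states no figure on this point, so there is nothing to reproduce. The check sets the texts side by side and then illustrates size under assumed rates.

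**Text**

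1. Protocol 10.1 and 10.3: record the syndrome, not its components.
2. Protocol 7.2.1.3: the components include pulmonary, hepatic and renal manifestations.
3. Protocol Summary and SAP 11.2 item 2: the diagnosis belongs to IDH inhibition, which CCR subjects do not receive as study treatment.
4. SAP 11.2: no rule carries IDH-DS symptoms into items 4, 5, 6 or 8, and no term list says whether the syndrome term falls inside them.
5. SAP 11.4 and 11.4.2: laboratory data are summarized by treatment group independently of AE coding, including Grade 3/4 abnormalities, shifts to worst grade, and clinically significant hepatic and renal changes. Table 5 there has no creatinine row, but creatinine is in the chemistry panel (Protocol 6.1) and so comes under the general chemistry summaries. No comparable source exists for pulmonary events.

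Steps 1 to 4 give the asymmetry. Step 5 confines most of it to Pulmonary Events.

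**Illustration A: IDH-DS events add to a common background.** Let b be the background pulmonary incidence, d the IDH-DS rate in AG-221 and s the share of IDH-DS with a pulmonary manifestation. All three are assumptions, and independence is assumed.

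- Incidence with IDH-DS symptoms counted = b + (1 − b)ds
- Missed share = (1 − b)ds / [b + (1 − b)ds]

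| b | d | s | (1 − b)ds | Full incidence | Missed share |
|---|---|---|---|---|---|
| 0.20 | 0.10 | 0.5 | 0.040 | 0.240 | 16.7% |
| 0.30 | 0.10 | 0.5 | 0.035 | 0.335 | 10.4% |
| 0.30 | 0.05 | 0.3 | 0.0105 | 0.3105 | 3.4% (grid minimum) |
| 0.20 | 0.15 | 0.8 | 0.096 | 0.296 | 32.4% (grid maximum) |

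The grid is b = 0.20, 0.30; d = 0.05, 0.10, 0.15; s = 0.3, 0.5, 0.8. The missed share exceeds 10% in 10 of the 12 cells with d of 0.10 or more.

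**Illustration B: equal true risk p in both arms.** Take the planned 158 per arm (Protocol 3.1.1). Counted AG-221 risk = p − ds.

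- p = 0.20: 0.20 × 158 = 31.6 subjects per arm.
- d = 0.05, s = 0.5: 0.20 − 0.025 = 0.175, or 27.7 subjects; apparent risk ratio 0.175/0.20 = 0.88.
- d = 0.20, s = 0.8: 0.20 − 0.16 = 0.04, or 6.3 subjects; apparent risk ratio 0.04/0.20 = 0.20.
- p = 0.30, same two corners: 0.275/0.30 = 0.92 and 0.14/0.30 = 0.47.

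The true ratio is 1 throughout. The 0.20 corner is extreme: it supposes that 0.16/0.20 = 80% of AG-221 subjects with a pulmonary event had it only as IDH-DS. Both illustrations assume that no component is also reported as its own AE, and that CCR loses nothing.

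**The case against.** - **The events are still counted as an AESI.** IDH-DS is item 2, and the common AESI summaries apply to it: all, related, serious, serious related, Grade 3 or higher, and time to first onset. Symptoms, steroid treatment and study drug actions are shown as well. This stands. A reader might infer that AG-221 pulmonary and renal toxicity leaves the AESI reporting altogether; the documents do not support that. Events move between headings, and only those the investigator diagnoses as IDH-DS move.
- **Exclusion from the organ items is not written down.** This stands. Without term lists for items 4 to 8, exclusion is the likely reading only. But the gap leaves the choice open, and a single syndrome term could not show which organ was involved anyway.
- **One recording rule covers both arms.** This stands. A reader might infer that the protocol sets a different attribution rule for each arm, or that CCR can lose no events. In fact a CCR event that belongs to some other recorded diagnosis is absorbed too. The asymmetry lies in which diagnoses are available. If absorption by other diagnoses is similar in the two arms, the tilt from IDH-DS remains.
- **Laboratory data protect the renal and hepatic comparison.** They do in part, as SAP 11.4 and 11.4.2 show. They do nothing for pulmonary events.
- **Adding CRF symptoms brings a bias of its own.** Dedicated symptom capture that in practice exists only for AG-221 would be set against ordinary AE reporting in CCR. Giving each organ the overall syndrome grade could also turn mild renal dysfunction into a Grade 3 renal failure. This stands and shapes the fix.
- **AESI summaries are descriptive.** SAP 11.2 specifies no test, and the multiplicity strategy in SAP 10.1 concerns efficacy. This limits the weight of the point.

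**Conclusion.** The point holds in limited form. Pulmonary, renal and hepatic events recorded as IDH-DS are likely to be missing from the organ-specific AESI counts for AG-221, while the same manifestations recorded as individual AEs in CCR are counted. Where this operates it favours AG-221, and mainly in Pulmonary Events.

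The size is unknown. The documents give no IDH-DS rate, no organ share and no background rate, so the ranges above show what assumed rates would imply and are not estimates. The conclusion rests on three conditions: that sites follow Protocol 10.1 and 10.3, that the undefined items 4 to 8 do not take in the differentiation syndrome term, and that components are not also reported separately. A reader might take the illustrated ratios as evidence that AG-221 toxicity is being hidden; nothing in the documents supports that. OS and the key secondary endpoints are unaffected. This is a cheap improvement to safety reporting.

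**What to change.** In SAP 11.2:

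1. Give the PT or SMQ list for AESI items 4 to 8, and state for each whether the differentiation syndrome PT is included.
2. Add a supportive by-arm table on the safety population. For Pulmonary Events, Acute Renal Failure and Hepatic/Hepatobiliary, count a subject once per category if the event was reported as an AE or recorded as an IDH-DS symptom on the CRF page. Show it beside the AE-only table, and keep the separate IDH-DS summaries.
3. Present any-grade incidence. Do not carry the overall IDH-DS grade over as the organ-event grade unless a grade was collected for the symptom itself.
4. Footnote that the differentiation syndrome page is dedicated symptom capture that in practice exists only for AG-221, so the two tables should be read together.

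The cost is SAP wording and one derivation from symptom data the SAP already plans to tabulate. The CRF is not among the documents, so the completeness of those pages needs checking. IDH-DS symptoms will appear in two tables, and the AG-221 organ-level counts will look slightly less favourable.

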11.3. Death

Cause of death will be collected in the CRF and will be summarized for all treated subjects with the following categories during on-treatment period and post-treatment period:

- Death from malignant disease under study, or complication due to malignant disease under study
- Death from adverse event (not otherwise specified)
- Death from other cause
- Death from unknown cause (not assessable or insufficient data)

A death listing will include deaths for all screened subjects during pre-treatment, on-treatment, and post-treatment period.

11.4. Clinical Laboratory Evaluations

Clinical laboratory results will be summarized descriptively by treatment group, which will also include a display of change from baseline. Laboratory values outside of the normal ranges will be identified. Normal ranges will be used to determine the categories of High, Low, and Normal for laboratory tests that have no severity grade.

Where multiple laboratory records exist for the same scheduled visit, the record closest to the scheduled clinical visit date will be summarized. If a record exists on the same day of a scheduled visit date, this record will be selected. If no such record exists then the closest record will be determined by first checking for a record with date one day before clinical record, then for a record one day after clinical record. If neither of these exist then check two days before clinical record, and then two days after clinical record. Follow a similar logic until a closest record can be found. If more than one record is selected using above process, then the record with sample type not equal to "U" will used. If a unique record still cannot be determined then an average of records fitting above criteria will be taken, and this will be used in summaries.

Clinically significant hematologic and non-hematologic laboratory abnormalities that meet Grade 3 or Grade 4 criteria according to the NCI CTCAE 4.03 will be summarized. Where applicable, shift to high values will be presented separately from shift to low value (e.g. leukocytosis and leukopenia). The worst grade during the treatment period will be summarized by treatment group and by cycle. Frequency distributions of CTC grade that shift from baseline to the worst grade during treatment period will be presented by treatment arm when data is applicable. Graphical display of select laboratory parameters over the course of the study will be provided where useful to assist in the interpretation of results.

Listings of all clinical laboratory data from central laboratory with abnormal flags will be provided by subjects and tests. Listings will also be provided for the local laboratory data.

11.4.1. Hematology

For specific haematological parameters (Hemoglobin, platelet counts, ANC, WBC, and RBC), the change from baseline to nadir value will be summarized by treatment group.

Shifts in CTCAE grades from baseline to worst grade will be summarized by treatment and by cycle.

11.4.2. Serum Chemistry

For serum chemistry parameters, the change from baseline will be summarized by treatment group and study visit. Change in total, direct and indirect bilirubin by UGT1A1 mutation will be analyzed.

Shifts in CTC grades from baseline to worst grade will be summarized by treatment and by cycle.

The proportion of subjects with clinically significant post-baseline change in hepatic, renal function and electrolytes will be assessed based on the criteria presented below.

Table 5 Serum Chemistry Changes of Interest

Laboratory Test	Parameters for any value and the last value
Alanine Aminotransferase (ALT)	CTCAE Grades ≥ 3
Aspartate Aminotransferase (AST)	CTCAE Grades ≥ 3
Total Bilirubin	CTCAE Grades ≥ 3
Total Bilirubin \geq Grade 2 and ALT \geq Grade 2	Composite of Total Bilirubin \geq Grade 2 and ALT \geq Grade 2 within 1 cycle of Total Bilirubin elevation
Total Bilirubin \geq Grade 2 and AST \geq Grade 2	Composite of Total Bilirubin \geq Grade 2 and AST \geq Grade 2 within 1 cycle of Total Bilirubin elevation
Potassium	Composite: Hypokalemia Grade ≥ 2 and $>15\%$ decrease from baseline Hyperkalemia Grade ≥ 3 and $>15\%$ increase from baseline
Phosphorus	Composite: Hyperphosphatemia $>$ ULN and $>25\%$ increase from baseline
Calcium	Composite: Hypocalcemia Grade ≥ 3 and $> 15\%$ decrease from baseline
Magnesium	Composite: Hypomagnesemia Grade ≥ 2 and $>25\%$ decrease from baseline
Uric Acid	Composite: Hyperuricemia $>$ ULN and $>25\%$ increase from baseline

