- Aspartate aminotransferase (AST)/serum glutamic oxaloacetic transaminase (SGOT) and alanine aminotransferase (ALT)/serum glutamic pyruvic transaminase (SGPT)  $\leq 3 \times$  upper limit of normal (ULN), unless considered due to leukemic organ involvement, following review by the Medical Monitor; and
  - Serum total bilirubin  $\leq 1.5 \times$  ULN, unless considered due to Gilbert's syndrome (eg, a gene mutation in UGT1A1) or leukemic organ involvement, following review by the Medical Monitor; and
  - Creatinine clearance  $> 30$  mL/min based on the Modification of Diet in Renal Disease (MDRD) glomerular filtration rate (GFR):  
$$\text{GFR (mL/min/1.73 m}^2\text{)} = 175 \times (\text{serum creatinine})^{-1.154} \times (\text{Age})^{-0.203} \times (0.742 \text{ if female}) \times (1.212 \text{ if African American})$$
9. Females of childbearing potential (FCBP)\* may participate, providing they meet the following conditions:
- Agree to practice true abstinence\*\* from sexual intercourse or to use highly effective contraceptive methods (eg, combined [containing estrogen and progestogen] or progestogen-only associated with inhibition of ovulation, oral, injectable, intravaginal, patch, or implantable hormonal contraceptive; bilateral tubal occlusion; intra-uterine device; intrauterine hormone-releasing system; or male partner sterilization [note that vasectomized partner is a highly effective birth control method provided that partner is the sole sexual partner of the FCBP trial participant and that the vasectomized partner has received medical assessment of the surgical success]) at screening and throughout the study, and for 4 months following the last study treatment (6 months following the last dose of cytarabine); and
  - Have a negative serum  $\beta$ -subunit of human chorionic gonadotropin ( $\beta$ -hCG) pregnancy test (sensitivity of at least 25 mIU/mL) at screening; and
  - Have a negative serum or urine (investigator's discretion under local regulations)  $\beta$ -hCG pregnancy test (sensitivity of at least 25 mIU/mL) within 72 hours prior to the start of study treatment in the Treatment Phase (note that the screening serum pregnancy test can be used as the test prior to the start of study treatment in the Treatment Phase if it is performed within the 72-hour timeframe).

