  - Chemistry panel including sodium, potassium, calcium, magnesium, chloride, phosphorus, CO2, bicarbonate, blood urea nitrogen (BUN), creatinine, glucose, albumin, total protein, alkaline phosphatase (ALP), bilirubin (total and direct), uric acid, lactate dehydrogenase (LDH), AST/SGOT, ALT/SGPT, gamma glutamyl transpeptidase (GGT), amylase and lipase
  - UGT1A1 gene mutation test performed on peripheral blood samples for diagnosis of Gilbert's syndrome (refer to the inclusion criterion regarding serum total bilirubin in Section 4.2)
- Assessing AEs [REDACTED] start when the subject signs the ICF
- Transfusion history including the type, number of units, reason, and date of transfusions for the 8 weeks prior to the start of study treatment

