### Elevated Serum Bilirubin

Hyperbilirubinemia is induced by enasidenib inhibition of UGT1A1, the enzyme responsible for the metabolism of bilirubin (a condition similar to Gilbert's syndrome).

Patients with Gilbert's syndrome genotype treated with enasidenib experienced earlier onset of bilirubin elevation following treatment initiation, as compared to patients with normal UGT1A1 genotype. With continuing treatment, maximum severity of bilirubin elevation was similar in patients with Gilbert's syndrome and patients with normal UGT1A1 genotype. Reference toxicities of hyperbilirubinemia during AG-221 treatment is described in Section 7.2.1.3, and dose modification due to hyperbilirubinemia Section 7.2.1.2.

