**Renal dysfunction during azacitidine therapy**

In previous studies, renal abnormalities ranging from elevated serum creatinine to renal failure and death were reported rarely in subjects treated with intravenous azacitidine in combination with other chemotherapeutic agents. In addition, renal tubular acidosis, defined as a fall in serum bicarbonate to < 20 mmol/L in association with an alkaline urine and hypokalemia (serum potassium < 3 mmol/L) developed in 5 subjects with CML treated with azacitidine and

etoposide. If unexplained reductions in serum bicarbonate (< 20 mmol/L) occur, the dose should be reduced by 50% on the next course. Similarly, if unexplained elevations in serum creatinine or BUN to  $\geq 2$ -fold above baseline values and above upper limit normal occur, the next cycle should be delayed until values return to normal or baseline and the dose should be reduced by 50% on the next treatment cycle. The reduced dose should be maintained during subsequent cycles that are given (unless toxicity develops).

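### SAP Table 5 has no renal-function row and no baseline condition in its liver rows, so it does not measure the post-baseline change it promises; its bilirubin composites are also less specific in the AG-221 arm

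*SAP*

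**What the plan says.** The lead-in to SAP Table 5 covers three domains and speaks of change after baseline: "The proportion of subjects with clinically significant post-baseline change in hepatic, renal function and electrolytes will be assessed based on the criteria presented below". The column heading is "Parameters for any value and the last value".

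The rows for ALT, AST and total bilirubin each read "CTCAE Grades ≥ 3". Two further rows are composites: total bilirubin Grade 2 or higher together with ALT (or AST) Grade 2 or higher, the transaminase finding falling "within 1 cycle of Total Bilirubin elevation". The remaining rows are potassium, phosphorus, calcium, magnesium and uric acid.

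Four places in the protocol bear on this.

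- Inclusion criterion 8 (Section 4.2) sets limits of 3 x ULN for ALT/AST and 1.5 x ULN for total bilirubin, then waives them. The transaminase waiver is for leukemic organ involvement. The bilirubin waiver is for Gilbert's syndrome ("a gene mutation in UGT1A1) or leukemic organ involvement, following review by the Medical Monitor").
- The chemistry panel in Section 6.1 includes creatinine, BUN and "bilirubin (total and direct").
- Section 7.2.1.3, under Elevated Serum Bilirubin, states: "Hyperbilirubinemia is induced by enasidenib inhibition of UGT1A1, the enzyme responsible for the metabolism of bilirubin".
- Section 7.2.2.1 has an azacitidine rule on renal dysfunction ("Similarly, if unexplained elevations in serum creatinine or BUN to" at least twice baseline and above the upper limit of normal).

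**The concern.** A lead-in that refers to criteria given below is a specification for the programmer. Where the table is silent, the criterion must be chosen later. Here that would happen in an open-label trial whose interim analysis is already complete. Where the table omits a condition that the lead-in states, the count does not match its label.

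The renal omission concerns an organ that the documents treat as important. Renal dysfunction is among the manifestations of IDH differentiation syndrome in Protocol 7.2.1.3. It has its own azacitidine subsection, and acute renal failure is an adverse event of special interest in SAP 11.2.

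The liver rows are at risk of counting abnormalities that were present at entry as on-study changes. The composites raise a separate question, that of specificity. A joint rise in transaminase and bilirubin is read as a sign of liver injury, but in one arm the study drug can supply the bilirubin half by a different route.

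**Working it through.** No sample size, event count or test enters this point, so the check is a row-by-row reading of Table 5 against its lead-in.

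| Table 5 row | Domain | Criterion | Baseline condition | Uses total bilirubin |
|---|---|---|---|---|
| ALT | liver | Grade 3 or higher | none | no |
| AST | liver | Grade 3 or higher | none | no |
| Total bilirubin | liver | Grade 3 or higher | none | yes |
| Total bilirubin with ALT | liver | Grade 2 or higher on both | none | yes |
| Total bilirubin with AST | liver | Grade 2 or higher on both | none | yes |
| Potassium | electrolyte | low: Grade 2 or higher; high: Grade 3 or higher | >15% change | no |
| Phosphorus | electrolyte | above ULN | >25% increase | no |
| Calcium | electrolyte | low: Grade 3 or higher | >15% decrease | no |
| Magnesium | electrolyte | low: Grade 2 or higher | >25% decrease | no |
| Uric acid | other | above ULN | >25% increase | no |

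Counts: renal-function rows, 0 of 10; liver rows with a baseline condition, 0 of 5; other rows with one, 5 of 5; liver rows using total bilirubin, 3 of 5. Both lipid rows in SAP Table 6 also require a change from baseline (>10%), so the liver rows are the exception among the change-of-interest tables.

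**Renal function.** There is no row for creatinine, BUN or clearance. Potassium, phosphorus and uric acid can move with renal function, but none measures it and the table does not present them as renal criteria. The proportion that the lead-in promises cannot be computed from Table 5, although the analytes are collected.

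**Liver rows.** Take a subject admitted under a criterion 8 waiver whose baseline value already meets the grade in a row. If the post-baseline values stay the same, both the any-value and the last-value rules are met with no change at all, so the subject counts towards a proportion labelled as change. The waivers state no upper bound. The documents do not reproduce the CTCAE grade cut-offs or say how many subjects were admitted by waiver, so the number affected cannot be calculated.

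**Composites.** Each needs two things: ALT or AST at Grade 2 or higher, and total bilirubin at Grade 2 or higher, linked by the one-cycle window. The protocol says enasidenib itself induces hyperbilirubinemia. The second condition can therefore be met in the AG-221 arm without hepatocellular injury, leaving the transaminase condition to decide the flag. SAP 11.4.2 separately analyses total, direct and indirect bilirubin by UGT1A1 mutation. That analysis is not joined to ALT or AST within a subject, and a split by mutation status does not isolate drug-induced inhibition in non-carriers.

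**The case against.** The strongest reply is that Table 5 is one descriptive display among many. Serum chemistry, which includes creatinine and BUN, is also to be summarized as change from baseline by arm and visit, as clinically significant Grade 3/4 abnormalities, as worst grade by arm and cycle, as baseline-to-worst grade shifts, and in flagged listings (SAP 11.4 and 11.4.2). SAP 11.2 adds special-interest summaries for acute renal failure, for bilirubinemia and liver safety, and for hepatic and hepatobiliary disorders. Absolute grades are a legitimate presentation, and the shift tables show baseline grade.

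Much of this stands. A reader might infer that only generic grade shifts are left for renal safety, but the list above shows otherwise. What it does not supply is the promised renal proportion, a liver count restricted to worsening, or a within-subject link between direct bilirubin and transaminases. The shift tables are single-analyte and the special-interest items are based on adverse events.

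Three stronger readings of the bilirubin point are also tempting and are not supported.

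- That any coincident transaminase rise completes a composite: Grade 2 or higher is required on both analytes.
- That the effect is confined to the AG-221 arm: subjects with Gilbert's syndrome may enter and be randomized to either arm.
- That the drug-induced rise is harmless: the protocol does not say so. Section 7.2.1.3 allows increases above 5 x ULN to be considered clinically significant even in UGT1A1 mutation carriers, and its bilirubin paragraph cross-refers to the reference toxicities and to dose modification.

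**Conclusion.** The point holds on two direct mismatches between lead-in and table: no renal-function criterion (0 of 10 rows), and no baseline condition in the liver rows (0 of 5, against 5 of 5 elsewhere in the table). As written, the liver rows can count a stable entry abnormality as a post-baseline change. This rests on at least one subject entering under a waiver at a qualifying grade, which the eligibility text permits but the documents do not quantify.

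The third element is one of specificity and does not contradict the lead-in. The two composites are less specific for liver injury in the AG-221 arm, and the ALT-only and AST-only rows are untouched. The documents give no rates of bilirubin or transaminase elevation by arm, so any count of excess flagged subjects would only return the rates assumed.

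The consequence is limited to the safety tables. No hypothesis test, alpha allocation, or result for OS, ORR or EFS depends on Table 5. It is still worth correcting, because the remedy is specific and cheap.

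**What to change.** In SAP Table 5:

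1. Require every liver row, single and composite, to be a worsening from the subject's own baseline grade, for each analyte in the row.
2. Add a pre-specified creatinine/BUN row relative to baseline, with a threshold chosen by the sponsor. The baseline-and-ULN wording in Protocol 7.2.2.1 is one available form. It is written there as an azacitidine dose-modification trigger for unexplained elevations, so it would be borrowed for analysis only. Alternatively, delete renal function from the lead-in and rely on the other renal outputs.
3. Keep the total-bilirubin composites and show direct-bilirubin versions beside them, by arm and UGT1A1 status, as a supportive display. The documents contain no direct-bilirubin threshold, so the sponsor would have to state one.

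The cost is a short SAP revision before the final database lock and a few more table rows. Creatinine, BUN, total and direct bilirubin, ALT, AST and UGT1A1 status are already collected, so no new visits or samples are needed.
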